In the acute effects study, qualified patients will come fasting to the research center. Review of study procedures and vitals will be performed. Insulin infusion (pump) will be stopped and basal blood, urine and adipose tissue biopsy samples will be obtained. Placebos, exenatide (5µg) or dapagliflozin (10mg) (with appropriate placebos) or combination of exenatide and dapagliflozin will be administered, according to a randomized fashion and cohort assigned, and blood samples will be collected every 30 min for up to 8 hours after starting the treatment. Urine will be collected every hour up to 8 hours and a second adipose tissue biopsy will be collected at 6 hours after the start of the treatment. Additional blood samples will be collected at 1, 2, 4 and 6 and 8 hour marks for MNC isolation. Plasma and mononuclear cell (MNC) fractions will be prepared from the blood samples. The patient will then come back at the 24 hour mark for a fasting blood and urine collection. The long term study will then commence. Depending on the cohort, Exenatide extended release or dapagliflozin (along with appropriate placebos) or a combination of both drugs will be started and continued for 12 weeks according to original randomization of day 0. In the long term study, dapagliflozin (or the appropriate placebo) will be started at 5mg dose and will be titrated to 10mg/day after 5 days. Fasting blood and 24hr urine samples will be collected at 1, 4 and 8 weeks. At 12 weeks, the 2nd acute effects testing study will be repeated as described above.

Drug Blinding:

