dapagliflozin 10mg (two 5mg) with appropriate placebos in a randomized fashion). Subjects will be fasting throughout the first 6 hr of the visit. Blood (10ml) will be collected every 30 min and spot urine every 1hr for up to 8 hours. Additional blood samples (20ml) will be collected at 1, 2, 4 and 6 and 8 hours for *MNC* isolation. A second adipose tissue biopsy will be collected at 360 min after starting the treatment. Basal insulin Infusion will be restarted at the end of the 360min sample collections, food will be provided, patient will be instructed to deliver a bolus insulin dose through bolus wizard calculator of the insulin pump after entering the grams of carbohydrates and blood glucose (Bolus wizard matches the bolus insulin dose based on individual patient's insulin to carbohydrate ratio and correction factor for high blood glucose). Patients will be monitored for at least 2hr before discharging from center (8hr time point). The subject's blood glucose and ketones ( $\beta$ -hydroxybutyrate) levels will be monitored every 30 minutes and ketones will be also measured in urine using Ketostix every hour to ensure safety. If the BG concentrations exceed 400 mg/dl or blood  $\beta$ -hydroxybutyrate exceeds 2.5mmol/l (or +3 (80mg/dl) or greater in urine) anytime during the 360 minutes following single dose/doses with or without clinical signs and symptoms of DKA like nausea and vomiting then STAT lab sample for CMP will be collected along with research blood sample. Spot urine and adipose tissue biopsy will be collected only if deemed feasible by the investigator present based on the clinical condition of the participant. Basal insulin will be restarted; bolus insulin as per the bolus wizard calculator will be administered and a meal provided. Patient will be discharged only after all laboratory parameters return to pretesting levels with no clinical symptoms of DKA.

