This will now mark the end of the acute testing phase and the beginning of the 12 weeks treatment phase. If the HbA1c is  $\geq 7.5\%$ ; then no reduction will be made in dose of insulin while if the HbA1c ranges from 7-7.5% then the basal and pre-prandial insulin doses will be reduced by 5%. All patients will be instructed on how to give the single subcutaneous injection of Exenatide extended release (2mg weekly) or Exenatide extended release placebo (for those in cohort 1), or open label drugs (for those in cohort 2), which will be administered at home the next day. Patients will also be provided with 12 oral tablets of either 5mg placebo or 5mg dapagliflozin (depending on their group assignment and cohort) and instructed to consume 1 tablet in the morning on each of the first 4 days and 2 tablets (10 mg) on days 5, 6 and 7 (and for the rest of the 12 weeks thereafter) and to return to the center on day 7. Urine collection container will be provided and patients instructed to collect 24hr urine before their next visit. The patients will be trained to recognize the symptoms of DKA and to self-test ketones daily and if they develop any symptoms consistent with DKA, including nausea, vomiting, fatigue, confusion, or shortness of breath. Information sheet about above information will be provided to participants. Patients will be instructed to measure ketone bodies in urine samples daily with Ketostix (Bayer) and record it in diary provided. If ketone bodies in urine measure +2 or greater ( $>4\text{mM}$  in urine), patients are required to notify the research center. The investigators will collect all necessary information and advise the patient of any steps to mitigate the risk of DKA or to visit the closest emergency department and to inform emergency staff of their participation in a research study.

;

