**Visit 6 (Week 12):** Subjects will be asked to come for the visit in a fasting state (10-12hr fasting). The will be fasting for the entire visit. Once the patient arrives to the research center, a complete physical examination will be done, 24hr urine will be collected, vitals and fingerstick blood glucose and ketones ( $\beta$ -hydroxybutyrate) using the Precision Extra glucose and ketones meter (Abbott Laboratories) will be measured. For MDI patients, baseline blood, spot urine, and adipose tissue will be collected. The remainder of this visits' procedures apply only to pump patients. An IV port will be placed in order to obtain blood samples throughout the duration of the visit. Insulin infusion will be stopped. Baseline blood, spot urine, and adipose tissue will be collected immediately after stopping insulin. One of the treatment arms will be administered to the patient according to their original group assignment as in Visit 2. All samples and monitoring procedures will be done as in Visit 2. Insulin doses will be titrated to target blood glucose between 70-180 mg/dl if

possible at all times without having additional hypoglycemia (less than 70 mg/dl) before discharge from study.

Phone calls will be made by our team at weeks 2, 6 and 10 to ensure safety. Patients will also be instructed to call if they develop unexpected symptoms.

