3. **Fat aspiration procedure:** Subcutaneous fat tissue aspiration will be performed on abdomen at a 10 cm distance from umbilicus. The subjects will not have taken aspirin or NSAIDS in the last 72 hours. If that is the case, then the procedure will not be done. The skin will first be prepared with povidone-iodine (Betadine) and alcohol. A sterile drape will be placed around the appropriate area. 3 cc of 1% lidocaine will then be administered subcutaneously. After adequate anesthesia has been achieved, approximately 20-50cc of 0.5% lidocaine will be injected in the adipose tissue. Dose of lidocaine will not exceed 4.5mg/kg body weight. Aspiration of fat tissue will then be performed with a 3-holed cannula (Tulip Instrumentation, length: 15cm, diameter: 2.1mm) fixed to a 10mL syringe. More than one attempt at aspiration can be done at the same site during the procedure to get adequate sample. After getting adequate fat tissue (500mg-3g), the puncture site will be pressed for at least ten minutes before the patient rises up from supine position (to minimize bruising). The study subjects will then be discharged home. The adipose tissue will be centrifuged to remove blood and fluid contaminants. The upper adipose tissue will be collected into a separate sterile tube, washed twice with cold sterile Phosphate Buffered Saline (PBS) and centrifuged to remove the PBS. The adipose tissue sample will be weighed and approximately 500 mg transferred to a separate tube for analysis. Total RNA, nuclear extracts and total cell lysates will be prepared from the adipose tissue.
4. **Quantification of HSL and SGLT2 Expression:** The mRNA expression is measured in MNC by RT-PCR: Total RNA was isolated from MNC and adipose tissue using commercially available RNAqueous®-4PCR Kit (Ambion, Austin, TX). One  $\mu$ g of total RNA is reverse transcribed using Advantage RT-for-PCR Kit

- (Clontech, CA). Real Time RT-PCR was performed using Stratagene Mx3000P QPCR System (La Jolla, CA), Sybergreen master mix (Qiagen, CA) and gene specific primers ([name]). The specificity and the size of the PCR products are tested by adding a melt curve at the end of the amplifications and by running it on a 2% agarose gel. All values were normalized to the expression of a group of housekeeping genes including actin, ubiquitin C and cyclophilin A.

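### No staff contact is scheduled after the Visit 6 fat biopsies except the pump patients' 24-hour sample return, so delayed biopsy-site harm is recorded only if the patient calls or a clinic record shows it

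*Combined protocol and SAP*

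**What the plan says.** Visit 6 (Week 12) is the last visit in the text of Section 10.1 and in the schedule table of Section 10.2. Pump patients repeat the acute test, with a fat biopsy at baseline and another at six hours. MDI patients have the baseline biopsy only, and Section 25.1 confirms one biopsy per test visit for them.

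- **Examination.** It precedes the biopsies: "Once the patient arrives to the research center, a complete physical examination will be done".
- **End of visit.** Insulin is titrated to target as far as "possible at all times without having additional hypoglycemia (less than 70 mg/dl) before discharge from study". Section 11.2 gives individual participation as 12 weeks.
- **Calls.** "Phone calls will be made by our team at weeks 2, 6 and 10 to ensure safety". Section 21.2 speaks of at least three calls during the study and ties none of them to the time after Visit 6.
- **24-hour return.** In the acute study, "The patient will then come back at the 24 hour mark for a fasting blood and urine collection". Section 10.2 confirms a 24-hour sample at week 12 as well as at week 0. It belongs to the acute test, so it applies to pump patients only.
- **Biopsy risk.** Section 21.1 expects site pain that may last one to two weeks, names infection and thrombosis as serious risks, and asks patients to call about marked pain or swelling. Section 21.2 says biopsy complications will be monitored.
- **Collection of safety data.** Section 19.4 relies on visits and telephone calls. Section 19.5 adds patient-initiated phone reports. Section 10.4 lists medical records as a source.

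**The concern.** The second set of biopsies is placed on the day the patient leaves the study. The period in which the protocol itself expects symptoms therefore lies almost wholly after scheduled safety collection has ended. After Visit 2 the same period contains a clinic visit and a safety call, each an occasion to ask about the site. After Visit 6 it contains neither.

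What is at stake is the completeness of the safety record for an invasive procedure done only for research, in a trial where Section 22.1 expects no benefit to the individual. A site infection, a thrombosis or prolonged pain that appears some days after Visit 6 would enter the data only through the patient's own call or a chance entry in a clinic record. The safety reviews in Section 19.6 can weigh such an event only once it has reached the team.

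Delayed harm from the six-hour insulin stop is a lesser matter. Insulin is restarted, patients are observed to eight hours and return at 24 hours. After a glucose or ketone threshold event, "Patient will be discharged only after all laboratory parameters return to pretesting levels with no clinical symptoms of DKA".

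**Working it through.** The protocol gives no figure to reproduce. The check lists every scheduled contact after each biopsy day and counts those in the period when site symptoms are expected.

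**Contacts after Visit 2 (day 0)**

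- Day 1: 24-hour return, pump patients only.
- Day 7 or 8: Visit 3, all patients. The Visit 2 text tells them "to return to the center on day 7"; the schedule table in Section 10.2 has day 8.
- Week 2, taken as day 14: safety call, all patients.

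**Contacts after Visit 6 (day 84)**

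- Day 1: 24-hour return, pump patients only.
- After that: none. The calls at weeks 2, 6 and 10 are over, no further visit exists, and participation is 12 weeks.

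| Scheduled staff contacts | After Visit 2 | After Visit 6 |
|---|---|---|
| Day 1, pump | 1 | 1 |
| Day 1, MDI | 0 | 0 |
| Days 2–14, pump | 2 | 0 |
| Days 2–14, MDI | 2 | 0 |
| Total to day 14, pump | 1 + 2 = 3 | 1 + 0 = 1 |
| Total to day 14, MDI | 0 + 2 = 2 | 0 + 0 = 0 |

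These are contacts. The protocol does not describe any of them as asking about the biopsy site.

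**Provisions that might fill the gap**

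- The minimum of three calls in Section 21.2 permits a fourth but does not schedule one.
- The review in Section 19.6 when a subject has finished all visits examines data already collected. It is not a patient contact.
- The end-of-study visit in Section 20.3 concerns withdrawals and is conditional.

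None adds a contact after Visit 6.

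**Number of biopsies in the uncovered period**

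Inputs: 80 patients (Section 5.1), 15% drop-out (Section 17.2), one biopsy per MDI patient and two per pump patient at Visit 6. The pump/MDI split is not given, so both extremes are shown.

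- No drop-out: 80 × 1 = 80 (all MDI) to 80 × 2 = 160 (all pump).
- All drop-out before Visit 6: 80 × 0.85 = 68 patients, so 68 × 1 = 68 to 68 × 2 = 136.

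These are ceilings. The fat aspiration procedure requires that "The subjects will not have taken aspirin or NSAIDS in the last 72 hours", failing which it is not done. After a threshold event during the acute test, "Spot urine and adipose tissue biopsy will be collected only if deemed feasible by the investigator present". The counts are of procedures, not of harms; the documents give no complication rate from which to estimate missed events.

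**The case against.** The facts are not in dispute; the objection is to their weight.

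**Monitoring promise.** Section 21.2 goes on to speak of monitoring at every visit, and Section 19.5 places collection at study visits, so neither clearly promises surveillance after the last one. But the every-visit wording in 21.2 attaches most naturally to volume control and hypoglycemia. The statement on biopsy complications carries no time limit, so setting the gap against it is fair.

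**The Visit 2 comparison.** The week-1 visit is timed to the dapagliflozin dose increase, and the week-2 call belongs to a series made during treatment. Neither was designed as biopsy follow-up. That stands: the contrast shows lost occasions to ask, not a biopsy check that was dropped.

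**Patient reporting.** Patients are told to phone as soon as any adverse event occurs, and reports are reviewed the same day. Research cover is described as year-round. Section 5.3 says most recruits come from the centre's own clinic, and continuing patients will generally have been through the procedure once. Infection and lasting pain usually announce themselves. This is a genuine partial safeguard, but it remains passive. No clinic appointment or records search after Visit 6 is planned, and some participants are recruited through advertising.

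**Consequence.** Biopsy complications are not among the safety endpoints in Section 19.3 and trigger no suspension rule in Section 19.9. No efficacy conclusion changes. This is correct and keeps the point modest.

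**Consent pages.** These are not available and might contain further instructions after biopsy. That cannot be checked.

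**Conclusion.** The concern holds. From day 2 after the Visit 6 biopsies no staff contact is scheduled for anyone, against two by day 14 after Visit 2. MDI patients have no contact at all after Visit 6; pump patients have one, at 24 hours, described as a sample collection. The stated symptom period of one to two weeks therefore rests on patient call-in and incidental records.

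At most 80 to 160 biopsies are affected, or 68 to 136 if 15% drop out before Visit 6. This assumes that every planned biopsy is done, that the 24-hour return applies only to pump patients, and that the week-2 call falls on day 14.

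The consequence is limited to the completeness of safety data. It is the same in all arms and leaves the primary analysis unchanged. It should be corrected because the remedy is cheap, not because the trial's conclusions depend on it.

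**What to change.** In Section 10.1, add one closing safety call about 14 days after Visit 6 for every patient, made by the team that already makes the week 2, 6 and 10 calls. Ask about:

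- the biopsy site (pain, swelling, infection);
- symptoms of ketosis or DKA, which adds little to the same call;
- any care received elsewhere.

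State in Sections 11.2, 19.4 and 19.5 that adverse events are collected until that call, and complete the per-subject review in Section 19.6 after it. Report events found this way with a flag showing that they arose after Visit 6, and leave the suspension percentages in Section 19.9 as they are.

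The cost is at most 80 short calls, or about 68 after drop-out, roughly one a week at the planned accrual of one subject weekly. Section 21.2 already allows more than three calls, and no extra visit, sample or staff member is needed. The drawbacks are that each record closes two weeks later and that the stated length of participation needs a protocol amendment, with possible changes to the consent wording or re-consent under Section 26.4.

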### **Procedures:**

1. **Ketone bodies measurements:** Serum and plasma samples will be collected from whole blood within 30 min and stored at -80C till analysis. Spot and 24 hr urine samples will be centrifuged and clear supernatant stored at -80C till analysis. Plasma and urine samples will be analyzed for ketone bodies using commercially available kits for  $\beta$ -hydroxybutyrate (Cayman Chemicals, Ann Arbor, MI) and for acetoacetate (Biovision, Malpitas, CA). Patients will be instructed to measure ketone bodies in urine samples daily with Ketostix (Bayer).
2. **MNC isolation:** Blood samples (30-40ml) is collected in Na-EDTA and carefully layered on Lympholyte medium (Cedarlane Laboratories, Hornby, ON) according to manufacturer's instructions. Samples are centrifuged and two bands separate out at the top of the RBC pellet. The MNC band was harvested and washed twice with Hank's balanced salt solution (HBSS). This method provides yields greater than 95% MNC preparation.
3. **Fat aspiration procedure:** Subcutaneous fat tissue aspiration will be performed on abdomen at a 10 cm distance from umbilicus. The subjects will not have taken aspirin or NSAIDS in the last 72 hours. If that is the case, then the procedure will not be done. The skin will first be prepared with povidone-iodine (Betadine) and alcohol. A sterile drape will be placed around the appropriate area. 3 cc of 1% lidocaine will then be administered subcutaneously. After adequate anesthesia has been achieved, approximately 20-50cc of 0.5% lidocaine will be injected in the adipose tissue. Dose of lidocaine will not exceed 4.5mg/kg body weight. Aspiration of fat tissue will then be performed with a 3-holed cannula (Tulip Instrumentation, length: 15cm, diameter: 2.1mm) fixed to a 10mL syringe. More than one attempt at aspiration can be done at the same site during the procedure to get adequate sample. After getting adequate fat tissue (500mg-3g), the puncture site will be pressed for at least ten minutes before the patient rises up from supine position (to minimize bruising). The study subjects will then be discharged home. The adipose tissue will be centrifuged to remove blood and fluid contaminants. The upper adipose tissue will be collected into a separate sterile tube, washed twice with cold sterile Phosphate Buffered Saline (PBS) and centrifuged to remove the PBS. The adipose tissue sample will be weighed and approximately 500 mg transferred to a separate tube for analysis. Total RNA, nuclear extracts and total cell lysates will be prepared from the adipose tissue.
4. **Quantification of HSL and SGLT2 Expression:** The mRNA expression is measured in MNC by RT-PCR: Total RNA was isolated from MNC and adipose tissue using commercially available RNAqueous®-4PCR Kit (Ambion, Austin, TX). One  $\mu$ g of total RNA is reverse transcribed using Advantage RT-for-PCR Kit

- (Clontech, CA). Real Time RT-PCR was performed using Stratagene Mx3000P QPCR System (La Jolla, CA), Sybergreen master mix (Qiagen, CA) and gene specific primers ([name]). The specificity and the size of the PCR products are tested by adding a melt curve at the end of the amplifications and by running it on a 2% agarose gel. All values were normalized to the expression of a group of housekeeping genes including actin, ubiquitin C and cyclophilin A.
5. **Western blotting:** MNC total cell lysates are prepared by suspending the cells in 150  $\mu$ L of lysis buffer (10mM Tris-HCl, 150mM NaCl, 0.2% Triton X and proteases and phosphatases inhibitors). After 30 min incubation on ice, samples are centrifuged at 12000 Xg for 10 min, supernatants are collected and total protein concentrations are determined. Sixty  $\mu$ g of total cell lysate are boiled in 2X SDS buffer (100 mM Tris-HCl, 4% SDS, 20% glycerol, 0.06 % bromophenol blue and 200 mM DTT), proteins separated by SDS-PAGE and then transferred to PVDF membrane. Polyclonal or monoclonal antibodies against SGLT2 and HSL, (Abcam, Cambridge, MA) and actin (Santa Cruz Biotechnology, CA) will be used and the membranes are developed using super signal, chemiluminescence reagent (Pierce Chemical, IL). Densitometry is performed using molecular analyst software (Biorad, CA) and all values are corrected for loading with actin.
  6. **Plasma glucose, insulin, glucagon, glycerol, HSL and FFAs measurements:** Glucose levels are measured in plasma by YSI 2300 STAT Plus glucose analyzer (Yellow Springs, Ohio). FFAs and glycerol levels are measured by a colorimetric assay (Roche, Richmond, VA) and (Cayman Chemicals, Inc) respectively. Active GLP-1 and glucagon will be measured using ELISA kit (Millipore, MA) from samples collected in DPP-IV inhibitor (Millipore, MA) and protease inhibitor cocktail (Sigma) to prevent GLP-1 and other peptides degradation. HSL assay in plasma and adipose tissue will be done using ELISA (Biomatik, Wilmington, DE). Cortisol, electrolytes, and catecholamines will be measured by standard assays by Quest Diagnostic Labs.

#### 10.2 Describe what data will be collected.

*NOTE: For studies with multiple data collection points or long-term follow up, consider the addition of a schedule or table in your response.*

#### *Response:*

Measurements of beta-hydroxybutyrate, acetoacetic acid, glucose, FFA and glucagon, will be measured from all blood samples collected. HSL, GLP-1, glycerol, electrolytes, serum bicarbonate, cortisol and catecholamines will be measured at 0, 60, 120, 240, 360, 480 min and at 24hr following single dose studies at 0 and 12 weeks visits and at baseline on the 1, 4 and 8 weeks visits. Ketone bodies will be measured in all urine samples. All MNC and adipose tissue samples will be tested for HSL and SGLT2 expression, as in the table below.

Visit #	Screening	1	2	3	4	5	6
Day #		-7	0	8 week 1	28 week 4	56 week 8	84 week 12
Study Procedures	Screening	Insulin titration	Single dose test	2 days after up titration			End long term/ Single dose test
History	X						
Physical	X				X		X
CBC	X						X
CMP/lipid profile	X				X		X
Vitals and BP	X	X	X	X	X	X	X
Pregnancy test	X				X	X	X
HbA1c	X						X
Plasma ketone bodies and metabolic end points			X	X	X	X	X
Urine ketone bodies and oxidative stress end points			X	X	X	X	X
Insulin injection log/Glucose/CGM/pump and food diary review/Insulin dose titrations		X Review of glucose/Insulin doses	X	X	X	X	X
Adipose tissue biopsy			X				X

 10.3 List any instruments or measurement tools used to collect data (e.g. questionnaire, interview guide, validated instrument, data collection form).

*Include copies of these documents with your submission.*

Response: Source documents will be used to collect patient information. The CGM or insulin pump will be used to collect glucose and insulin data, Glucose and ketone meter will be used to measure glucose and ketone in blood. Ketostix for measuring ketones in urine. Food diary will be used to collect food intake.

10.4 Describe any source records that will be used to collect data about subjects (e.g. school records, electronic medical records).

Response: electronic medical records and research files.

10.5 Indicate whether or not **individual** subject results, such as results of investigational diagnostic tests, genetic tests, or incidental findings will be shared with subjects or others (e.g., the subject's primary care physician) and if so, describe how these will be shared.

Response: Individual participant lab results will be disclosed to the participant upon their request. If the participant requests documentation be shared with another physician, physician office or hospital the participant must come to the research center to collect said documentation or the documentation can be mailed to their given home address.

10.6 Indicate whether or not **study** results will be shared with subjects or others, and if so, describe how these will be shared.

Response: Not Applicable. Study results will not be shared with the subjects. However, unidentifiable study results could be published in the form of a manuscript or abstract and will be reported to Astra Zeneca and to clinicaltrials.gov

